6.5. Procedures

- **6.5.1.a. Item pool generation.** Focus groups and cognitive interviews will refine item generation of the planned "dementia action test" relating key FLOW items with hypothetical scenarios and expressed behavioral intent. Included will be measures demonstrating self-efficacy and attitudes, including relevant elements of the Dementia Attitudes Scale⁵³
- **6.5.1.b.** "Go With the FLOW" Cartoon development. A 3-minute program cartoon similar in style to our Hip Hop Stroke cartoons¹ will be developed and mapped to our existent song of the same title (See Supplemental File: Lyrics), related comics, and character icons (see **Figure 5**) focusing on the FLOW mnemonic and primary behavioral outcomes.
- **6.5.1.c.** School selection/recruitment. The Office of School Wellness of the New York City Department of Education and local school district Superintendents will collaborate with Investigators to identify NYC schools with similar demographics, excluding schools having already participated in our programs. School Principals will be invited to participate in the research study during face-to-face presentations of the intervention and control programs. During this meeting, a specially developed 10-minute explanatory promotional video will explain the OSHH intervention and show the curriculum and program objectives, and guestions will be answered.
- **6.5.2. Selection/recruitment of children.** Children in 4th and 5th grades in participating schools will be identified from school rosters along with their parents, who will be contacted via telephone or in-person at school events by research team for the purposes of informed consent (occurs three months prior to the start of data collection).
- **6.5.3. Selection/recruitment of parent.** To maintain statistical independence, only one adult from each family will be interviewed. Rather than arbitrarily targeting whichever parent happens to answer the phone or is met inperson, we will ask the parent to identify the adult ("parent") in the household ("household" may include relatives) who is most likely to have been the target of the child's dementia-information communications.
- **6.5.4.** Baseline knowledge assessment in parents. Parents who have given consent will be contacted inperson at school events or by telephone one month later, and a baseline dementia knowledge questionnaire will be administered following a brief health literacy survey (see Section 6.6-6.7 for details). We will assess parental knowledge of key signs and symptoms of dementia and the correct course of action through questions identical to those used for the pre-testing of their children.
- **6.5.5. Randomization to arm.** The data coordinating center has developed randomization algorithms to incorporate rolling enrollment which will be applied as schools will be contacted on a rolling basis over the 5 year study period. The investigators will not be told which arm any given school is assigned until after the baseline assessments have been completed. It is not possible to blind to condition, once intervention has been assigned.
- **6.5.6.** Baseline knowledge assessment in children. Around one month after the baseline knowledge assessment in parents, all participating children in both arms of the trial will attend a session to be held in the school auditorium, during which children's knowledge concerning dementia symptoms and response will be assessed (see Sections 6.6-6.7 for details).
- **6.5.7. Implementation of the intervention/control.** The intervention and control conditions will be implemented immediately following the children's' pretest knowledge assessment. Certified lay health facilitators will conduct the intervention or usual care program in 1-hour sessions, over three consecutive days, in schools assigned to the either the intervention or control arm. An immediate post-test will be administered at the end of the third day to children in both the intervention and control arms.
- **6.5.8. 1-week follow-up data collection (parents).** One week after the completion of the 3-day intervention and control programs, follow-up surveys will be conducted in-person at school or, when that is not possible, by telephone (with a telephone protocol of up to five telephone contact attempts if necessary). These surveys assess: (1) Has the child told parent about participating in OSHH at school and discussed dementia with them? and (2) Does the parent recall *what* the child communicated regarding the symptoms and recommended action? To assess these, the research surveyor will use a structured interview format (See Sections 6.6-6.7).

- **6.5.9.a. 3-month follow-up data collection (children).** Three months following the 3-day intervention and control programs, students will be assembled once more in school auditoriums by program facilitators for a delayed post-test after which the educational booster sessions will be provided to students. Children in both conditions will participate in 30-minute review sessions; children in the intervention arm will see the OSHH material; those in the control arm will review the "usual care" material.
- **6.5.9.b. 3-month follow-up data collection (parents).** Three months following the completion of the intervention and control programs, a second survey will be conducted (in-person or, when that is not possible, by telephone) on parents to assess long-term retention of the materials.

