6.8. Power Calculations and Analyses

Power calculations were performed for the primary aim of evaluating the effect of the intervention on the parent-level recognition of AD symptoms post-test and at three months post intervention. The outcome was treated as both continuous and binary for the most conservative test of meaningful change.

6.8.1. Design Features: The design is a cluster randomized trial with random assignment of 10 schools to each of two arms. Subjects will be nested within schools and classrooms. We posit a relatively lower intracluster correlation coefficient (ICC) for schools than for classrooms. Estimates have been adjusted for unreliability of the outcome (estimated at R=0.70) and clustering. The variance inflation factor (V_{if}) =1.87, assuming that n_e (the average number of subjects within a class) =20; the intracluster correlation coefficient for class (ICC_{class}) =0.03 and for school (ICC_{school})=0.015; N_s (5th and 6th grade classes) =2. The pooled σ (standard deviation) is estimated at 1.06, based on our prior work. Assuming a two-tailed test with σ =0.05, power (1- β =80%), n=400 parents per group will be adequate to detect posited effect sizes shown below.

6.8.2.Power and Analyses for 3 Level Cluster Sampling and Evaluation of Pre- and Post-Intervention, Treating AD Symptom Recognition as Continuous: Power calculations were from the perspective of least detectable group differences in rates of change (slopes), adjusted for the design effects of correlations induced by repeated measures of subjects nested within classrooms and schools. Different scenarios regarding correlations among the repeated outcomes were considered. The mixed model for rate of change in outcome: $y_{ijk} = \beta_0 + \beta_k T_{ij} + FU_{lm}$, (equation 1) where ijk refers to subjects, time points and group; FU_{lm} is the random effect associated with school and class; T=0 is the pre-test and immediate post-test and T=1 is the 3 month post-test. The sample size formula for the rate of change⁵⁵ is: $m = \frac{2(z_\alpha + z_\beta)^2 \sigma^2 (1-\rho)}{ns_\alpha^2 d^2}$, with m=m*V_{if}/R;⁵⁶

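### No masking is planned for the surveyors who take the primary parent outcome at 1 week and 3 months, although partial masking looks possible

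*Combined protocol and SAP*

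**What the plan says.** Section 6.5.5 protects the baseline: "The investigators will not be told which arm any given school is assigned until after the baseline assessments have been completed". The same section then says "It is not possible to blind to condition, once intervention has been assigned" and names no role.

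Section 6.8 gives the primary aim used for the power calculation as "evaluating the effect of the intervention on the parent-level recognition of AD symptoms post-test and at three months post intervention". The parent data come from surveys:

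- At 1 week (6.5.8), "follow-up surveys will be conducted in-person at school or, when that is not possible, by telephone", and "the research surveyor will use a structured interview format".
- At 3 months (6.5.9.b), "a second survey will be conducted (in-person or, when that is not possible, by telephone) on parents". No assessor is named.

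Delivery belongs to a different named role (6.5.7): "Certified lay health facilitators will conduct the intervention or usual care program in 1-hour sessions".

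One topic of the 1-week survey is "Has the child told parent about participating in OSHH at school and discussed dementia with them". Section 6.6.2 says that the child's communication is assessed in both arms.

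No section plans masked surveyors or explains why they could not be masked.

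**The concern.** Children, facilitators and schools must know which program is running. A person who interviews a parent need not. The plan treats knowledge of arm as a risk at baseline, then says nothing to protect the follow-up interviews, where the primary outcome is measured.

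An interviewer who knows the arm may prompt, wait or record answers differently. If that happened, follow-up scores would be affected and baseline scores would not. Adjusting for the pretest removes baseline differences, and random effects for school and class absorb random clustering. Neither removes a systematic shift by arm, so it would be read as a treatment effect.

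**Working it through.** **Roles and exposure to arm**

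- Facilitators deliver the programs (6.5.7) and necessarily know the arm.
- A research surveyor collects the 1-week parent data (6.5.8). The 3-month assessor is not specified (6.5.9.b).
- Research staff or the research team also meet principals and recruit parents (6.2.3), contact families for consent (6.5.2) and carry out fidelity checks and video review (6.4.b). The documents do not say whether these people are also the surveyors.
- The communication topic is covered in both arms (6.6.2), so its presence reveals nothing. A parent's answer can reveal the arm.

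Separate role names and a telephone route make some masking plausible. In-person interviewing at school, which comes first at 1 week, makes complete masking unlikely.

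**Reproducing the plan's scale**

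Inputs from 6.8.1: SD 1.06, reliability R = 0.70, 20 subjects per class, 2 classes per school, ICC 0.03 for class and 0.015 for school, 400 parents per arm, two-sided 0.05, power 80%. From Table 2: detectable difference 0.315 points at correlation 0.4 with a1 = 0.

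1. Variance inflation: 1 + (20 − 1)(0.03) + (2 − 1)(20)(0.015) = 1 + 0.57 + 0.30 = 1.87, as stated.
2. Parents per arm: 2(1.96 + 0.8416)² × 1.06² × (1 − 0.4²) / 0.315² × 1.87 / 0.70 = 399, against 400 stated. Power at 400 is 0.801.
3. Standard error of the adjusted difference: √[2 × 1.06² × (1 − 0.4²) × (1.87 / 0.70) / 400] = 0.112 points.

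**Illustration of a bias (sizes assumed; the documents give none)**

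With no true effect and a differential shift b, the two-sided rejection probability is Φ(b/SE − 1.96) + Φ(−b/SE − 1.96).

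| Assumed b (points) | b in SD | Correlation 0.4, SE 0.112 | Correlation 0.7, SE 0.0875 |
|---|---|---|---|
| 0 | 0 | 0.050 | 0.050 |
| 0.05 | 0.047 | 0.073 | 0.088 |
| 0.10 | 0.094 | 0.145 | 0.208 |

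This applies to the pretest-adjusted 3-month comparison with the plan's large-sample standard error. It shows how sensitive the test is to a small shift. It does not show that a shift exists.

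**The case against.** The strongest reply is that the interview leaves little room for bias. It is structured. The parents' baseline questions are the same as the children's pretest questions (6.5.4), and the child instrument is multiple choice with listed signs and two distractors (6.6.1). If the same items are used at follow-up, which the documents do not state outright, there is little for a surveyor to code. This stands as a reason to expect a limited bias. It does not cover the 1-week question about what the child communicated, which may need probing.

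A second reply is that the blinding sentence names no role and follows one about investigators, so reading it as covering surveyors is an inference. That is correct, but the gap remains on either reading, because masking of surveyors is not planned anywhere.

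A third reply is that the questionnaire's wording and order are not in the documents, so knowledge items may already come first. That is possible. The plan should then say so.

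Some stronger readings are tempting and should not be drawn:

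- *Surveyors can be kept fully unaware with existing staff.* Staff numbers and overlap of roles are not described, and in-person contact at school exposes the arm.
- *The OSHH item by itself gives the arm away.* The topic is covered in both arms. Only the answer can disclose the arm.
- *An assumed shift in pass rate can be expressed as a share of the planned 16.7 points.* Section 6.8.3 defines that figure as the 3-month difference minus the immediate post-test difference. An equal shift at both follow-ups would cancel in it, so the ratio is not meaningful.

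**Conclusion.** The point holds as a gap in design that can be partly closed. The plan makes an unqualified statement about blinding and provides no masking for those who collect the primary parent outcome. Partial masking looks possible and would not disturb the design.

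No bias has been shown, and its size is unknown. Under the assumed shifts of 0.05 to 0.10 points at correlation 0.4, the two-sided type I error would be about 0.07 to 0.145 instead of 0.05. That rests on the plan's own SD, reliability, variance inflation and sample size, and on a shift that favors one arm at 3 months. The conclusion that surveyors could be masked in part rests on the separate naming of surveyors and facilitators and on the telephone option. It does not rest on any described staffing.

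**What to change.** - Limit the sentence in 6.5.5 to children, facilitators and schools. State who surveys parents at 1 week and at 3 months, and whether they are masked. If masking is judged infeasible, give the reason.
- Give surveyors contact sheets that carry IDs and no arm.
- Where current staffing allows, do not assign a surveyor to parents of a school where that person delivered, attended or fidelity-checked sessions.
- Ask all knowledge items before the communication item, and word that item neutrally, for example as a health program at school.
- Record the surveyor's guess of arm at the end of each interview, so that readers can judge how far masking held.

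The cost is changes to forms, contact sheets and scheduling. Separating roles may be hard if few staff are available, which the documents do not let us judge. Masking will be incomplete, especially for in-person interviews at school. Sample size (400 parents per arm), alpha and power stay as they are.

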6.6. Outcome Measures

- **6.6.1. Dementia Symptom and Response Knowledge Assessment (student).** We will use similar instruments to those in our OSHH pilot study²⁷ to replicate our findings by assessing children's pre- and post-test knowledge of AD symptoms and recommended action. Multiple choice questions will be given to assess knowledge of (1) dementia localization (Where in the body does Alzheimer disease occur?(brain) In which part of the brain does Alzheimer disease happen? (Remembering part) What part of the brain helps you remember? (Hippocampus) (2) Recognition of 6 key signs/symptoms (Forgetting words and familiar faces and names; Losing things all the time; Overlooking chores like paying the bills and cleaning; Writing things down all the time; Having trouble counting out the right amount of money when paying; Having trouble using household appliances like a remote control or microwave) plus two distractors (Chest pains, Facial droop), (3) Response to symptoms presented in a hypothetical scenarios in which the dementia diagnosis is not given (considered normal aging v. concerning for dementia (and needs to be seen by physician), (4) assessment of the FLOW mnemonic, (5) self-efficacy for dementia recognition, and (6) ability to formulate the correct action plan in response to recognizing dementia
- **6.6.2.** Assessment of child's communication to parent about dementia signs/symptoms. This measure assesses whether the child has talked with one of the adults in the household in both the OSHH and control arms concerning symptoms of dementia and correct response.

6.7. Baseline measures

- **6.7.1. Demographic Form.** Includes age, sex, and race of children and parents; also educational status, income, sex, and age of parents and caregivers; and number of adults in household. Measures of school-level economic need are available in the public domain via the NYC Department of Education.
- **6.7.2. Literacy Questionnaire** We will assess health literacy of parents prior to baseline assessment of dementia symptoms knowledge. We will use a rapid bilingual (English and Spanish) screening tool that identifies patients at risk for low health literacy, called the "Newest Vital Sign", and has been validated by clinical studies.⁵⁴

6.8. Power Calculations and Analyses

Power calculations were performed for the primary aim of evaluating the effect of the intervention on the parent-level recognition of AD symptoms post-test and at three months post intervention. The outcome was treated as both continuous and binary for the most conservative test of meaningful change.

6.8.1. Design Features: The design is a cluster randomized trial with random assignment of 10 schools to each of two arms. Subjects will be nested within schools and classrooms. We posit a relatively lower intracluster correlation coefficient (ICC) for schools than for classrooms. Estimates have been adjusted for unreliability of the outcome (estimated at R=0.70) and clustering. The variance inflation factor (V_{if}) =1.87, assuming that n_e (the average number of subjects within a class) =20; the intracluster correlation coefficient for class (ICC_{class}) =0.03 and for school (ICC_{school})=0.015; N_s (5th and 6th grade classes) =2. The pooled σ (standard deviation) is estimated at 1.06, based on our prior work. Assuming a two-tailed test with σ =0.05, power (1- β =80%), n=400 parents per group will be adequate to detect posited effect sizes shown below.

6.8.2.Power and Analyses for 3 Level Cluster Sampling and Evaluation of Pre- and Post-Intervention, Treating AD Symptom Recognition as Continuous: Power calculations were from the perspective of least detectable group differences in rates of change (slopes), adjusted for the design effects of correlations induced by repeated measures of subjects nested within classrooms and schools. Different scenarios regarding correlations among the repeated outcomes were considered. The mixed model for rate of change in outcome: $y_{ijk} = \beta_0 + \beta_k T_{ij} + FU_{lm}$, (equation 1) where ijk refers to subjects, time points and group; FU_{lm} is the random effect associated with school and class; T=0 is the pre-test and immediate post-test and T=1 is the 3 month post-test. The sample size formula for the rate of change⁵⁵ is: $m = \frac{2(z_\alpha + z_\beta)^2 \sigma^2 (1-\rho)}{ns_\alpha^2 d^2}$, with m=m*V_{if}/R;⁵⁶

 $s_{x}^{2} = \sum (t_{j} - \bar{t}) = 0.667 \ V_{if} = (1 + (n_{e} - 1)\rho_{e})(1 + (n_{s} - 1)\rho_{s}n_{e}\rho_{e}/(1 + (n_{e} - 1)\rho_{e})) \ , \ \text{where} \ n_{e} \ \text{is the number of subjects}$ within class, n_s is the number of classes within schools, rho e is the ICC for classes, rho s is the ICC for school.⁵⁷ For different values of p_{rm} (the average correlation of the repeated outcome measures, we provide detectable rates of change and accompanying Cohen's d effect sizes. For ρ_m=0.4, the detectable rate of change (β₁=0.29) over 3 months from the model in equation (1) translates to a Cohen's d (endpoint difference between the intervention and control group/pooled standard deviation) of 0.27 or for ρ_m=0.6, β₁=0.27 and Cohen's d=0.25. Given the above scenarios, we will be able to detect relatively small effect sizes in terms of endpoint differences between the intervention and control groups. The Ancova model using a pretest score as covariate will improve power. The formula is $y_{iik} = y_{i0k} + \beta_0 + \beta_{ik} + FU_{lm}$ where y_{i0k} is pretest score for subject i in group k and j is the time point (j=1 for immediate post-test and j=2 for the 3 month post-test). Assuming the intervention group improves by δ (Cohen's d= δ/σ) over the control group at the 3 month post-test, we can use different weights for the immediate post-test in calculating power (a₁=0 indicates no increased test performance for the intervention as contrasted with the control group at immediate post-test, a₁=1/2 indicates 50% increased performance of the intervention over the control group, and a₁=1 indicates 100% increased performance of the intervention as contrasted with the control group). The sample size formula for the Ancova model⁵⁸ is: $m = \frac{2(z_a + z_\beta)^2 \sigma^2 (1 - r_b^2)}{2 \sigma^2 (1 - r_b^2)}$ with m=m*V_{if}/R, $r_b^2 = \sum (a_i r_{ij}) / \sqrt{\sum \sum a_i a_j r_{ij}}$, $\Delta = \sum (a_i d_j) / \sum \sum (a_i a_j r_{ij})$. As shown in **Table**

2, smaller effect sizes are detectable under the scenario that there is some improvement immediately as well as at 3 months.

Table 2. Power Analyses for Ancova.									
Correlation	a ₁ =0	a ₁ =1/2	a ₁ =1						
ρ=0.4	δ=0.315 (d=0.300)	δ=0.210 (d=0.200)	δ=0.158 (d=0.149)						
ρ=0.5	δ=0.298 (d=0.281)	δ=0.199 (d=0.188)	δ=0.149 (d=0.141)						
ρ=0.6	δ=0.275 (d=0.259)	δ=0.184 (d=0.174)	δ=0.138 (d=0.130)						
ρ=0.7	δ=0.246 (d=0.232)	δ=0.164 (d=0.154)	δ=0.123 (d=0.116)						

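### The detectable slope given for correlation 0.4 (0.29, d = 0.27) does not follow from the plan's formula, which gives 0.326 (d = 0.31); power at 0.29 is about 70%, not 80%

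*Combined protocol and SAP*

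**What the plan says.** Section 6.8 states that the power calculations serve the primary aim, parent-level recognition of symptoms. Section 6.8.1 sets the common inputs: a two-tailed test at 0.05, class and school clustering summarised as "The variance inflation factor (V_{if}) =1.87", an outcome reliability of 0.70, and an SD for which "The pooled σ (standard deviation) is estimated at 1.06, based on our prior work". It concludes: "power (1- β =80%), n=400 parents per group will be adequate to detect posited effect sizes shown below".

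Section 6.8.2 gives a sample size formula for the difference in slopes and reports the smallest detectable slope under two assumed correlations among the repeated measures. For 0.4 it gives "the detectable rate of change (β₁=0.29) over 3 months", converted to d = 0.27. The second case reads "or for ρ_m=0.6, β₁=0.27", with d = 0.25.

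**The concern.** Only the correlation changes between the two scenarios, and the formula fixes how the detectable slope must move with it. The two reported slopes are too close together, so at least one is wrong.

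The suspect figure is the 0.4 case, the less favourable of the two and the one a reader would use to judge worst-case sensitivity for the primary aim. Section 6.8.3 also treats 0.4 as the conservative choice of correlation for the binary analysis. If the 0.4 slope is understated, the plan claims 80% power for an effect at which it has less.

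**Working it through.** **Inputs.** From 6.8.1: two-sided α = 0.05 (the symbol is printed as σ), power 80%, m = 400 per group, σ = 1.06, Vif = 1.87, R = 0.70. From 6.8.2: measurement times coded 0, 0, 1, and a time sum of squares of 0.667, since (1/3)² + (1/3)² + (2/3)² = 2/3.

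**Formula.** Section 6.8.2 gives m = 2(z_α + z_β)²σ²(1−ρ) / (time sum of squares × β²), then multiplies m by Vif/R. Solved for the slope:

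β = √[ 2(z_α + z_β)² σ² (1−ρ)(Vif/R) / (m × 0.667) ]

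**Step 1: a check that needs no constants.** Everything except (1−ρ) cancels, so β(0.4)/β(0.6) = √(0.6/0.4) = 1.225. The stated ratio is 0.29/0.27 = 1.074. The largest ratio that two-decimal rounding permits is 0.295/0.265 = 1.113. No choice of α, Vif, R, σ, m or time coding can reconcile the pair.

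**Step 2: which entry is wrong.** The common part is 2 × (1.960 + 0.8416)² × 1.06² = 17.64, Vif/R = 1.87/0.70 = 2.671, and 400 × 2/3 = 266.7.

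- ρ = 0.6: β = √(17.64 × 0.4 × 2.671 / 266.7) = 0.266, d = 0.266/1.06 = 0.251. The stated 0.27 and 0.25 reproduce.
- ρ = 0.4: β = √(17.64 × 0.6 × 2.671 / 266.7) = 0.326, d = 0.307. The stated 0.29 and 0.27 do not reproduce.

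A slope of 0.29 would correspond to 1−ρ = 0.6 × (0.29/0.3256)² = 0.476, a correlation of about 0.52.

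**Step 3: check of the shared inputs against Table 2.** For the a₁ = 0 column, with 1−ρ² as the variance factor, δ = √[17.64 × (1−ρ²) × 2.671 / 400].

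| ρ | Recomputed δ | Table 2 δ |
|---|---|---|
| 0.4 | 0.315 | 0.315 |
| 0.5 | 0.297 | 0.298 |
| 0.6 | 0.275 | 0.275 |
| 0.7 | 0.245 | 0.246 |

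The agreement confirms two-sided α, Vif = 1.87, R = 0.70 and m = 400. Dividing the two formulas gives slope/δ = √[1.5/(1+ρ)]. Table 2's own entries therefore imply a slope of 0.315 × √(1.5/1.4) = 0.326 at ρ = 0.4 and 0.275 × √(1.5/1.6) = 0.266 at ρ = 0.6.

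**Step 4: consequence at ρ = 0.4.** The standard error is 0.3256/2.8016 = 0.1162. Power at 0.29 is Φ(0.29/0.1162 − 1.960) = Φ(0.535) = 70.4%. Taking d = 0.27 instead gives 69.2%. For 80% power at 0.29, m = 400 × (0.3256/0.29)² = 504.2, so 505 per group.

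**Step 5: other readings.**

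| Reading | β at ρ = 0.4 | β at ρ = 0.6 |
|---|---|---|
| Stated in the plan | 0.29 | 0.27 |
| Inputs as stated | 0.326 | 0.266 |
| One-sided 0.05 | 0.289 | 0.236 |
| Vif from the printed formula, 1.579 | 0.299 | 0.244 |
| 0.667 multiplied again by n = 3 | 0.188 | 0.154 |

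The printed Vif formula evaluates to 1.57 × (1 + 0.015 × 20 × 0.03/1.57) = 1.579. The stated 1.87 results when the 0.03 in the second factor is left out. With 1.579, power at 0.29 is 77.5%.

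**The case against.** The inconsistency itself is hard to dispute; the argument is over what follows from it.

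- **A detectable effect is not a target.** Section 6.8.2 reports what a fixed sample can detect, and 400 per group is not derived from 0.29. This stands in part: the 505 figure measures the size of the error and does not show that the trial is too small. But 6.8.1 says 400 per group is adequate at 80% power for the effects listed, and for this one it is not.
- **The practical change is small.** Table 2 already shows d = 0.300 for ρ = 0.4 and a₁ = 0, close to the corrected 0.307, and the plan's description of these effects as relatively small survives. This stands, and it limits the weight of the point.
- **Table 3 is unaffected.** It uses a different formula for a binary outcome. This also stands. The link is only that 6.8.3 calls the same correlation conservative.
- **The ratio does not show which entry is wrong, and the formula needs interpretation.** The denominator is read here as 0.667 in total, and the printed Vif formula disagrees with 1.87. A one-sided z reproduces the 0.4 entry. However, that contradicts the stated two-tailed test and loses the 0.6 entry. The reading used here reproduces the 0.6 slope, and the other shared inputs reproduce the a₁ = 0 column of Table 2. How the error arose is unknown.

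**Conclusion.** The concern holds. The two slopes cannot both come from the plan's formula, whatever constants are used. On the stated inputs the 0.4 entry is the wrong one: the detectable slope is 0.326 (d 0.31), 12% above the stated 0.29 (d 0.27), and power at 0.29 is about 70%.

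That the pair is inconsistent rests on the formula alone. The corrected value rests on Vif = 1.87, R = 0.70, σ = 1.06, a two-sided 0.05 test and a total time sum of squares of 0.667. The error is confined to this one scenario. The 0.6 slope and the a₁ = 0 column of Table 2 stand; Table 3 was not recomputed.

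**What to change.** In 6.8.2, restate the correlation 0.4 entry as a detectable slope of 0.33 (d = 0.31) and keep 0.27 (d = 0.25) for 0.6. Alternatively, keep 0.29 and give its power as 70%. In the same edit, state that 0.667 is the full time sum of squares, and bring the printed Vif formula into line with the stated 1.87.

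The main correction changes two numbers. The cost is a slightly less favourable sensitivity claim; sample size, conduct and analysis do not change.

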6.8.4. Secondary Aims

Analyses of Correlates and Predictors of AD Recognition: Treating the outcome as continuous, relationships with variables such as economic need, educational attainment and other demographic variables will be examined using a mixed model similar to that described above for continuous outcomes.

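### Parent education and health literacy are collected at baseline but left out of the parent ANCOVA; naming them in advance would add a small amount of precision at almost no cost

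*Combined protocol and SAP*

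**What the plan says.** Sections 6.8.2 and 6.8.3 set out three models for the parent outcome: a rate-of-change mixed model, an ANCOVA, and a logit mixed model for passing. All three carry group or time terms and a school and class random effect. Only the ANCOVA has a baseline covariate, the parent's own pre-test: "The Ancova model using a pretest score as covariate will improve power".

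Section 6.7 provides other baseline predictors. The demographic form (6.7.1) records parents' educational status. On health literacy (6.7.2), "We will assess health literacy of parents prior to baseline assessment of dementia symptoms knowledge", using the Newest Vital Sign. On schools (6.7.1), "Measures of school-level economic need are available in the public domain via the NYC Department of Education".

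Economic need and education come back only under the secondary aims (6.8.4), where "relationships with variables such as economic need, educational attainment and other demographic variables will be examined". Health literacy appears in no analysis. Three other provisions touch on covariates: interaction terms for moderators that are not named (6.8.3), a covariate for attrition bias that is not named, and propensity scores if the arms turn out substantially unbalanced (both 6.8.5). None of them is a precision covariate fixed in advance.

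**The concern.** The plan already relies on covariate adjustment for power, and it treats education as a candidate predictor of AD recognition. It puts the reliability of the outcome at 0.70, so a single pre-test is a noisy measure of what a parent knew beforehand. Education and health literacy may carry information about that underlying level which the pre-test misses.

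What is at stake is efficiency. The ANCOVA as written is valid, and no bias or error-rate problem follows from leaving these variables out. But the design sits at about 80% power for its tabulated differences, and the data will be in hand anyway. Naming the covariates now also avoids choosing them after the arms have been compared, which the conditional propensity-score provision leaves open.

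**Working it through.** **Inputs (section 6.8.1).** "The design is a cluster randomized trial with random assignment of 10 schools to each of two arms". "Assuming a two-tailed test with σ =0.05, power (1- β =80%), n=400 parents per group will be adequate" (0.05 is the two-sided significance level). The plan takes ICCs of 0.03 for class and 0.015 for school, with 20 parents per class, two classes per school and V_if = 1.87. The SD is 1.06 and the reliability R is 0.70.

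**Step 1: reproduce the plan's figures.**
- V_if = 1 + 19×0.03 + 20×0.015 = 1.87, as stated. This takes 0.015 as the correlation between parents in different classes of one school.
- Detectable difference = (1.960 + 0.842) × 1.06 × √[2(1−ρ²) × 1.87 / (0.70 × 400)].
- For ρ = 0.4, 0.5, 0.6 and 0.7 this gives 0.315, 0.297, 0.275 and 0.245. Table 2 (a₁ = 0) has 0.315, 0.298, 0.275 and 0.246. The stated power therefore already includes the pre-test.

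**Step 2: room left by the pre-test.** The unexplained share is 1−ρ², which is 84% at ρ = 0.4 and 51% at ρ = 0.7. Not all of it can be explained by other variables: if R = 0.70 means that 30% of observed variance is measurement error, about 54% (84−30) to 21% (51−30) is open to any baseline predictor.

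**Step 3: where parent covariates act.** Splitting 1.87 gives:
- school: 40×0.015 = 0.60 (32%)
- class: 20×(0.03−0.015) = 0.30 (16%)
- parent: 0.97 (52%)

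**Step 4: gain from parent covariates.** Let e be the share of parent-level variance they explain beyond the pre-test. The documents give no value, so e is an assumption. It is taken to have no effect on the school and class parts. The variance ratio is [0.90 + 0.97(1−e)]/1.87, and normal-quantile power is Φ(2.802/√ratio − 1.960).

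| e | Variance ratio | Detectable difference smaller by | Power, normal | Power, t with 18 df |
|---|---|---|---|---|
| 0 | 1.000 | – | 80.0% | 75.5% |
| 2% | 0.990 | 0.5% | 80.4% | 75.9% |
| 5% | 0.974 | 1.3% | 81.0% | 76.6% |
| 10% | 0.948 | 2.6% | 82.0% | 77.7% |

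If the same covariates also explained 10% of school variance (e = 2%), normal-quantile power would be 81.7%. At 25% of school variance (e = 5%) it would be 84.2%. These too are assumptions.

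**Step 5: what e requires.** Suppose the covariates have the same combined correlation c with pre-test and post-test. Then e = c²(1−ρ)/[(1+ρ)(1−c²)]. At ρ = 0.5 this is c²/[3(1−c²)], so e = 2% needs c of about 0.24 and e = 10% needs c of about 0.48. In simulations where a parent covariate predicted only the stable level behind a noisy pre-test, the standard error of the arm effect fell by about 0% to 7% and did not rise materially.

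**Step 6: a school-level covariate instead.** It acts on the 32% school part, leaves 17 degrees of freedom, and inflates the variance by about 1 + 1/16 through chance correlation with arm. Power on t quantiles, against 75.5%, with assumed school and parent R²:
- 0% and 5%: 73.8%
- 10% and 2%: 74.5%
- 10% and 5%: 75.2%
- 25% and 10%: 78.5%

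**The case against.** The strongest reply is that the plan already adjusts for the most relevant predictor and that nothing in the documents shows a loss. Education and health literacy may mainly predict the stable knowledge level that the pre-test captures. Simulating that case with a school covariate and a parent covariate added together made the ANCOVA standard error about 1% worse. The gain is also confined mainly to the ANCOVA: in the change-score contrast, adding both covariates moved the standard error between about 4% worse and 4% better.

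Much of this stands. The size of the gain rests on assumed values, and it is small or nil in the rate-of-change model. The possible loss, however, comes largely from the school-level covariate, which uses one of 18 degrees of freedom and can be correlated with arm by chance. Parent-level covariates vary within schools and cost almost no school-level degrees of freedom.

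A reader might infer that economic need should also go into the main model because school and class dominate the variance. The documents do not support that. School and class are 48% of the variance of the arm difference (0.90/1.87; 39% to 56% under other readings of the ICCs and the reliability adjustment), but only 3% of the variance of the parent score itself (4.5% if the two ICCs are added). Sections 6.2.2 and 6.5.1.c select schools with similar demographics, which narrows the spread of economic need. Step 6 shows that power can fall when its R² is low.

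**Conclusion.** The point holds as a modest improvement to the ANCOVA. Two parent-level predictors are collected and left unused in the arm comparison, and one of them, health literacy, is used nowhere. Under assumed incremental values of 2% to 10%, the detectable difference shrinks by 0.5% to 2.6% and power rises by about 0.4 to 2 points, with more only if the covariates also explain differences between schools.

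A reader might also infer that the trial is giving up a large amount of power, such as a 13% to 21% cut in variance. That would need school-level R² of 25% to 50% together with parent-level R² of 10%, all beyond the pre-test and before any cost for degrees of freedom or chance imbalance. The documents give no basis for such values.

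**What to change.** In section 6.8.2, for the ANCOVA of the continuous parent score:
- Pre-specify fixed effects for parent pre-test, parent education and Newest Vital Sign score, and state how the last two are coded. Keep the school and class random effects.
- State one simple rule for missing covariate values, applied identically in both arms and without reference to the outcome.
- Report the pre-test-only model as supportive.
- Add one school-level covariate (economic need or school-mean parent pre-test, chosen now) as a sensitivity analysis only.

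This is a change of wording. It needs no new data and no further enrolment. The cost is the missing-covariate rule and slightly more analysis work.
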